1. LIST OF ABBREVIATIONS

AE	Adverse Event
AFP	Alpha-Fetoprotein
ALT	Alanine Aminotransferase
ALP	Alkaline Phosphatase
AST	Aspartate Aminotransferase
BSA	Body Surface Area
BUN	Blood Urea Nitrogen
cfDNA	Circulating Free DNA
CI	Confidence Interval
Cmax	Maximum plasma Concentration
CR	Complete Response
CSR	Clinical Study Report
CT	Clinical Trial
CTCAE	Common Terminology Criteria for Adverse Events
CT Scan	Computerized tomography scanner
DBP	Diastolic Blood Pressure
DLT	Dose Limiting Toxicity
DLTES	Dose Limiting Toxicity Evaluable Set
DNA	Deoxyribonucleic Acid
DoR	Duration of Response
DSMB	Data Safety Monitoring Board
DSUR	Development Safety Update Report
eCRF	electronic Case Report Form
ECG	Electrocardiogram
ECOG PS	Eastern Cooperative Oncology Group Performance Status
ES	Enrolled Set
FIH	First in Human
(γ) -GT	Gamma - Glutamyl Transferase
HCC	Hepatocellular Carcinoma
HR	Heart Rate
ICH	International Conference on Harmonisation
INR	International Normalized Ratio

Statistical Analysis Plan

LDH	Lactate Dehydrogenase
LLN	Lower Limit of Normal
MeDRA	Medical Dictionary for Regulatory Activities
MPS1	Monopolar Spindle 1 kinase
MTD	Maximum Tolerated Dose
MRI	Magnetic Resonance Imaging
NCI CTCAE	National Cancer Institute Common Terminology Criteria for Adverse Events
OR	Overall Response
ORR	Overall Response Rate
OS	Overall Survival
PD	Progressive Disease (unless otherwise specified in the text)
PK	Pharmacokinetic
PFS	Progression Free Survival
PR	Partial Response (unless otherwise specified in the text)
QTc	Corrected Fridericia QT Interval
RECIST	Response Evaluation Criteria In Solid Tumors
RP2D	Dose Recommended for further Phase II investigations
SAP	Statistical Analysis Plan
SBP	Systolic Blood Pressure
SD	Standard Deviation (unless otherwise specified in the text)
SOC	System Organ Class
TEAE	Treatment Emergent Adverse Event
TLG	Table Listing and Graph
TKI	Tyrosine kinase Inhibitor
TTK	Tyrosine/Threonine Kinase
TS	Treated Set
ULN	Upper Limit of Normal
WBC	White Blood Cells

2. PURPOSE OF THE STATISTICAL ANALYSIS PLAN

This Statistical Analysis Plan (SAP) version 2.0, describes the planned Phase I analysis, Phase II interim and final analyses and reporting for MPSA-153-001 Clinical Trial (CT). All analyses take origin from the specifications in the statistical section of the CT Protocol version 5.0 (9-Jan-2023). Details of changes of the SAP version 2.0 respect to the first version, created based on CT Protocol version 2.0 dated 28-Jan-2021, are reported in Section [2.1](#).

Of note, this SAP does not cover the pharmacokinetic (PK) data analyses, described in the Protocol. These analyses are covered in a separate document written by Accelera S.r.l.

The structure and content of this SAP provide sufficient detail to guarantee compliance with the requirements identified by the International Conference on Harmonisation of Technical Requirements for Registration of Pharmaceuticals for Human Use (ICH): E9 Guidance on Statistical Principles in Clinical Trials and Integrated Addendum to E9(R1) [\[1\]](#).

The planned analyses identified in this SAP may be included in future abstracts, presentations and manuscripts, and may also support other documents, e.g. Development Safety Update Report (DSUR). Exploratory analyses not necessarily identified in this SAP may be performed to support planned analyses. Any post-hoc or unplanned analyses not specified in this SAP will be clearly identified as such in the Clinical Study Report (CSR).

The following documents were reviewed when preparing this SAP:

- CT Protocol version 5.0 (09-Jan-2023)
- CT Specific Case report forms (CRFs) Blank version 5.3 (23-Jun-2023)
- E9 - Statistical Principles for Clinical Trials [Integrated Addendum to E9(R1)] [\[1\]](#)
- E6(R2) - Guidance on Good Clinical Practice [Integrated Addendum to E6(R1)] [\[1\]](#)
- E3 - Guidance on Structure and Content of Clinical Study Reports [\[1\]](#)
- Applicable NMS procedural documents

2.1. Changes to Previous Version

The following changes are made in the current version 2.0 of the SAP:

- SAP re-written using new template (version T1_02, 17-May-2023). The mock-ups of tables, listings and graphs and algorithms are provided as separated Appendix using a new template (version T2_02, 17-May-2023).
- Section [3](#) Study Objectives and Endpoints was modified based on updated definition of primary efficacy objective and endpoint for Phase II and inclusion of additional secondary and exploratory endpoints.

Statistical Analysis Plan

- Section 4 Study Design, specifically Overview, Subject Selection and Sample Size, was modified based on the updated Phase II design.
- Section 5.2 Planned Schedule for Interim Analyses was modified based on the updated Phase II design that includes also a safety monitoring rule.
- Section 7, was updated to add clarifications for the definition of Evaluable Set for Phase II portion based on protocol version 5.0.
- Section 8 General Specification for Statistical Analysis, was mainly updated to include secondary phase II efficacy endpoints based on mRECIST evaluation.
- Section 9.7 Efficacy Analyses and Sections 9.7.1 Primary Efficacy Endpoint and 9.7.2 Secondary Efficacy Endpoints, were updated.
- Section 9.8.5 was updated to include additional ECG parameters collected for patients enrolled in Phase II.

3. STUDY OBJECTIVES AND ENDPOINTS

3.1. Objectives

3.1.1. Primary Objective(s)

- To determine the Maximum Tolerated Dose (MTD) and Recommended Phase 2 Dose (RP2D) of NMS-01940153E administered as single agent to adult patients with unresectable hepatocellular carcinoma (HCC) previously treated with systemic therapy (Phase I).
- To assess the anti-tumor efficacy of NMS-01940153E administered as single agent to adult patients with unresectable hepatocellular carcinoma previously treated with systemic therapy (Phase II).

3.1.2. Secondary Objective(s)

- To define the safety and tolerability profile of NMS-01940153E.
- To evaluate the pharmacokinetics of NMS-01940153E and its main metabolite NMS-03593478 in plasma and, limited to Phase I, also in urine.
- To evaluate additional measures of antitumor efficacy of NMS-01940153E.

3.1.3. Exploratory Objective(s)

- To explore correlation among Alpha-Fetoprotein (AFP) levels changes with NMS-01940153E exposure and clinical outcomes.
- To explore correlation among baseline tumoral and clinical prognostic factors with clinical outcome.

- To explore the potential correlation of selected molecular alterations in circulating free DNA (cfDNA) at baseline with clinical outcome.

3.2. Endpoints

3.2.1. Primary Endpoint(s)

- Drug related Dose Limiting Toxicities (DLTs) (Phase I).
- Objective Response Rate (ORR). The ORR will be calculated as the proportion of evaluable patients who have achieved, as best overall response (BOR), confirmed complete response (CR) or partial response (PR) measured by investigator-assessed RECIST 1.1 (Phase II).

3.2.2. Secondary Endpoint(s)

- Overall safety profile of NMS-01940153E characterized by type, severity (graded using NCI CTCAE Version 5.0), duration of the adverse events (AEs) and laboratory and ECG abnormalities, and relationship of the AEs to study treatment in the first and subsequent cycles of therapy.
- Pharmacokinetic parameters of NMS-01940153E and its main metabolite NMS-03593478 in plasma and urine (urine only in Phase I).
- Objective Tumor Response (Partial and Complete Response) as measured by investigator-assessed RECIST 1.1 (Phase I).
- Objective response rate as measured by investigator-assessed mRECIST (Phase II).
- Duration of response (DoR) as measured by investigator-assessed RECIST 1.1. and investigator-assessed mRECIST.
- Progression Free Survival (PFS), including landmark analyses, as measured by investigator-assessed RECIST 1.1.
- Overall survival (OS).

3.2.3. Exploratory Endpoint(s)

- Evaluation of AFP plasma levels.
- Evaluation of tumoral and other clinical prognostic features at baseline.
- Assessment of selected molecular alterations in circulating free DNA (cfDNA) at baseline.

4. STUDY DESIGN

4.1. Overview

Statistical Analysis Plan

This is a Phase I/II, open-label, non-randomized, multicenter study to explore safety, tolerability and antitumor activity of NMS-01940153E as single agent in adult patients with unresectable HCC previously treated with systemic therapy.

An independent Data Safety Monitoring Board (DSMB) will provide study oversight through periodic safety evaluations and make recommendations on study progress in the transition from Phase I to Phase II and at the planned interim analysis for the futility of Phase II.

The Phase I portion is designed as a dose-escalation study in sequential cohorts of patients aimed to obtain the MTD that is defined based on the DLTs observed in the first cycle of treatment.

The safety profile of NMS-01940153E administered IV on days 1, 8, 15 every 4 weeks has been characterized in the FIH, dose escalation study, conducted in adult patients with advanced/metastatic solid tumors up to the dose of 135 mg/m²/week. This dose was not defined as MTD in study 2014-002023-10 (EudraCT), since only one patient experienced DLT (Grade 3 fatigue) out of 6 evaluable patients.

Once the MTD is identified and the safety profile of NMS-01940153E has been reviewed by the Investigators, the Sponsor and the independent DSMB and is considered adequate based on the entire Phase I data available, the Phase II portion of the study will start.

The Phase II portion is designed as a two-stage study with an interim analysis for futility and stopping criteria for unacceptable toxicity to assess the antitumor activity of NMS-01940153E in adult patients with unresectable HCC previously treated with systemic therapy measured as objective response rate. In the Phase II portion, patients will receive the RP2D defined in the Phase I portion of the study as starting dose. Patients will be enrolled in continuous, and continuously evaluated for endpoints, with a futility analysis and stopping criteria for unacceptable toxicity performed as described in Section 5.2. The enrollment will be stopped in the event of futility as described in Section 5.2, with no more than 20 subjects treated overall until non-futility can be declared, if appropriate. In any case, the Sponsor may stop or pause enrollments any time during the study based on safety, efficacy or strategic reasons.

4.2. Subject Selection

This is a Phase I/II study in adult patients (>=18 years) with unresectable HCC, disease relapsed or refractory to the standard of care treatment not exceeding 3 lines of prior systemic treatment. For the Phase I portion subjects intolerant to previous treatment with tyrosine kinase inhibitors (TKIs) are eligible.

Statistical Analysis Plan

For the Phase II portion subjects must have disease relapsed or refractory to the standard of care treatment including an immunocheckpoint inhibitor as first line and at least a TKI, with no more than 3 prior lines of systemic therapies.

4.3. Sample Size

An overall sample size of approximately 55 patients may be anticipated considering both phases of the study.

For the Phase I, approximately 12-15 treated patients may be expected. Since the trial design foresees that sequential dose-escalation steps are applied to cohorts of 3 to 6 patients up to the identification of the MTD, the number of patients who will be enrolled and treated may vary, depending upon the toxicity observed that will influence cohort size and number of dose levels tested.

For the Phase II, the investigator-assessed objective response rate by RECIST 1.1. [2] will be the primary outcome measure. The sample size is based on precision considerations for the estimate of the primary efficacy endpoint. A single-group design will be used to obtain a one-sided 95% lower-limit confidence interval for a single proportion. The sample proportion is assumed to be 0.3. To produce a confidence interval with a distance from the sample proportion to the lower limit of no more than 0.12, 38 patients will be needed. A lower bound of 18% for ORR by RECIST would be meaningful relative to second line therapies in HCC. The emergence of atezolizumab with bevacizumab in first line has obscured true current second line outcomes with regorafenib, lenvatinib or sorafenib but it is logical to assume second line ORR would be no better relative to the pre-atezolizumab/bevacizumab era in which sorafenib was the first line standard. Prior to the atezolizumab/bevacizumab era, regorafenib in second line showed ORR of 11% by RECIST1.1 [3] and cabozantinib 4% [4], nivolumab 15% [5], pembrolizumab 18% [6] and apatinib 10.7% [7]. Therefore, in the third line setting following failure of atezolizumab/bevacizumab in first line followed by TKI in second line, and where current third line standards are not yet defined, it is reasonable to expect historical ORR no higher than 18%. Accounting for a 10% proportion of non-evaluable patients and if the stopping rule for futility is not met, up to 43 patients could be required for completing the trial, as reported in detail in Section 5.2; however, the Phase II part of the study will not enroll beyond 40 subjects unless discussed and agreed with FDA or relevant health authority, based on emerging response rates.

4.4. Treatment Allocation (and Blinding)

Not applicable

5. OVERVIEW OF PLANNED ANALYSES

5.1. Independent Data Monitoring Committee (IDMC) / Independent Data Safety Monitoring Board (DSMB)

An independent DSMB will provide study oversight through periodic safety evaluations and make recommendations on study progress in the transition from Phase I to Phase II and at the planned interim analysis for the futility of Phase II.

During the Phase I part, teleconferences will be held at the end of each cohort between the Investigators and the Sponsor to review all relevant safety and PK data and take decision on the dose escalation to be applied to the next cohort of patients. Once the MTD is identified, and the safety profile of NMS-01940153E has been reviewed by the Investigators, the Sponsor and the independent DSMB and is considered adequate based on the Phase I data available, the RP2D will be defined and the Phase II portion of the study will start.

Two clinical experts in the field of hepatology or onco-hepatology and a statistician, who are not involved in the study and have no conflict of interest with respect to study results, will compose the independent DSMB.

Tasks of the independent DSMB will be:

- To provide a recommendation on study progress in the transition from Phase I to Phase II and at the planned interim analysis for the futility of Phase II, based on risk-benefit evaluation;
- To periodically review adverse events, serious adverse events and all other safety and pharmacokinetic data collected during the study;
- To suggest other toxicities to be recorded/monitored in the group of patients who will be enrolled after the independent DSMB safety evaluation.

5.2. Planned Schedule of Interim Analyses

In the Phase II part of the study an interim evaluation for futility will be undertaken as soon as the first 10 evaluable patients will be enrolled and the data for primary efficacy endpoint analysis will be available including observations through at least 3 months with at least 1 on treatment tumor assessment by RECIST 1.1 [2]. If less than 1 responder i.e., patients who achieved CR or PR as best overall response, are observed, the study will be terminated for futility. This futility decision must be taken before 20 subjects total are enrolled otherwise enrollment will pause at 20 subjects until non-futility can be declared (if applicable). If at least 1 unconfirmed or confirmed responder is observed and there are no safety limitations, patients' enrollment will continue and proceed up to an overall enrollment of 38 evaluable patients or 40 total patients. For the safety monitoring, if two

or more patients on study experience Grade 4 adverse events the study will be put on hold to evaluate whether to continue or if additional risk mitigation is warranted. The independent DSMB will review the interim results and provide a recommendation on the study progress.

5.3. Final Analyses and Reporting

All final planned analyses identified in the protocol and in this SAP will be performed only after the last patient has completed the last visit scheduled, including follow-up and the clinical database has been cleaned and locked.

The mock-ups tables, listings and graphs for reporting purpose of CT MPSA-153-001 are reported in the separate appendix “Tables, Listings and Graphs Mock-ups and Algorithms”.

6. CHANGES IN THE PLANNED ANALYSIS

Not applicable

7. ANALYSIS POPULATIONS

Phase I Dose Escalation

Enrolled Set (ES): this population will include all patients who are enrolled in Phase I part, regardless of whether patients receive study treatment or not. This population will be evaluated in the analysis of patients' disposition.

Treated Set (TS): this set will include all enrolled patients who take at least one dose of NMS-01940153E. This population will be evaluated in the analysis of patients' disposition, baseline characteristics, treatment exposure, safety and efficacy.

Dose-Limiting Toxicity Evaluable Set (DLTES): this set will include all patients who receive in the first cycle at least 66% of study drug, unless the reason for non-compliance is drug-related toxicity, and undergo a DLT assessment within the DLT window. Patients not fulfilling one or more of aforementioned criteria will not be considered evaluable for MTD determination and will be substituted.

Phase II Part

Enrolled Set (ES): this population will include all patients enrolled in Phase II, regardless of whether patients receive study treatment or not. This population will be evaluated in the analysis of patients' disposition.

Treated Set (TS): this set will include all enrolled patients who actually receive at least one dose of NMS 01940153E. This population will be evaluated in the analysis of patients' disposition, baseline characteristics, treatment exposure and safety.

Evaluable Set (ES): this is the patient population for the primary efficacy analysis. This set will include patients of the TS who have measurable disease at baseline assessed according to RECIST 1.1 and at least one tumor evaluation on treatment, unless they die before the first tumor on-treatment assessment (i.e. if the patients died within 61 days from the start of the treatment considering that the first on treatment tumor assessment is foreseen at the end of cycle 2 with a time window of -2/+5 days), in which case they will be considered treatment failure. Moreover, subjects must have disease relapsed or refractory to the standard of care treatment including an immunocheckpoint inhibitor as first line and at least a tyrosine kinase inhibitor, not exceeding 3 lines of prior systemic treatment. Patients who received the RP2D defined in phase I portion as starting dose and from cycle 2 a dose increment of 25% (as per protocol version 4.0 dated 30-Jun-2022) were considered not evaluable for efficacy analysis (intra-patient dose escalation no more applicable as per protocol version 5.0). In detail, the evaluable population for primary efficacy endpoint will consist of a subset of the evaluable population up to the total number of subjects pre-determined by the interim for futility and final analyses. This means that, if the number of evaluable subjects exceeds the planned total number of subjects at either stage, the exceeding subjects will not be considered for primary efficacy analysis. Subjects will be counted into the primary evaluable population, consecutively, based on the date of first NMS-01940153E administration.

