Patients that cannot be retreated for any reason within 1 week from day 28 (up to day 35) will go off-treatment, unless the investigator believes treatment continuation is in the patient's best interest. In this case a maximum delay of 2 weeks (up to day 42) will be allowed. Otherwise patients may continue on investigational drug until disease progression, unacceptable toxicity, withdrawal of consent by the patient or other discontinuation criteria described in the protocol are met.

Phase I Dose Escalation

The safety profile of NMS-01940153E administered IV on days 1, 8, 15 every 4 weeks has been characterized in the FIH, dose escalation study, conducted in adult patients with advanced/metastatic solid tumors up to the dose of 135 mg/m²/week. This dose was not defined as MTD in study 2014-002023-10 (EudraCT), since only 1 patient experienced DLT (Grade 3 fatigue) out of 6 evaluable patients.

Considering the possible different tolerability in patients with compromised liver, the proposed starting dose for the Phase I portion of the study is 100 mg/m²/week, which is an intermediate dose level between the highest (135 mg/m²/week) and the next lower dose level (67.5 mg/m²/week) tested in the FIH study. According to the observed safety profile, dose increments of 25-35% will be applied to the proposed starting dose, until the MTD is reached. In presence of unacceptable toxicity observed at 100 mg/m²/week, a lower dose level by 25-35% may be tested.

Patients experiencing DLT during the DLT window can be retreated according to the time delay and dose modification schema.

No intra-patient dose escalation will be allowed.

Phase II

In the Phase II portion of the study, patients will be treated at the RP2D defined in the Phase I portion, as starting dose.

Phase I Dose Escalation

A conventional 3+3 study design with inter-individual dose-escalations will be adopted. Patients will be allocated to sequential cohorts of progressively higher dose levels of NMS-01940153E based on the presence of Dose Limiting Toxicities (DLT).

At each dose level, a minimum of 3 patients will be included.

If 0/3 patients experiences first cycle DLT, the next cohort will start one dose level higher.

If 1/3 patients experiences first cycle DLT, up to three more patients will receive the study medication at the same dose level; if 1/6 patients experiences first cycle DLT the next cohort will start one dose level higher.

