9.2.3.2. Re-treatment Criteria and Cycle Delay

A new cycle of treatment may begin when hematological and non-hematological toxicities are Grade ≤ 1 or have recovered to baseline values.

If these conditions are not met, treatment should be delayed for 1 week to allow for recovery. If, after 1-week delay, re-treatment criteria are met, then the new cycle can be initiated with a starting dose defined based on the toxicities observed in the previous cycle as outlined in the [Table 6](#).

If, after this period, toxicities do not recover to the pre-defined level, the patient will be withdrawn from the treatment, unless the Investigator believes treatment continuation is in the patient best interest. In this case, a maximum delay of 2 weeks (up to day 42 from cycle start) will be allowed.

Table 6. Dose Reductions/Treatment Discontinuations for NMS-01940153E Based on the Worst Grade (as per NCI CTCAE Criteria, Version 5.0) Observed During a Treatment Cycle and in the Prior Treatment Cycle

Toxicity	Dose Adjustment during treatment cycle	Next cycle Starting Dose
Hematological Toxicities		
Neutropenia Grade 3	Omit dose; when resolved to \leq Grade 1 within the same cycle, decrease one dose level.	Start at or maintain the decreased dose level.
Neutropenia Grade 4	Omit dose; when resolved to \leq Grade 1 within the same cycle, decrease one dose level.	Start at or maintain the decreased dose level.
Febrile Neutropenia	Omit dose; when resolved, decrease one dose level.	Start at or maintain the decreased dose level.
Thrombocytopenia Grade 3 associated with bleeding or thrombocytopenia Grade 4	Omit dose; when resolved to \leq Grade 2 within the same cycle, decrease one dose level.	Start at or maintain the decreased dose level.
Anemia Grade 3	Omit dose; when resolved to \leq Grade 2 within the same cycle, decrease one dose level.	Start at or maintain the decreased dose level.
Anemia Grade 4	Study treatment discontinuation.	Study treatment discontinuation.
Other Grade 3 Hematologic Toxicities	Omit dose; when resolved to \leq Grade 2 within the same cycle, decrease one dose level.	Start at or maintain the decreased dose level.
Other Grade 4 Hematologic Toxicities	Study treatment discontinuation.	Study treatment discontinuation.
Nausea and/or Vomiting		
Grade \geq 3 despite optimal management of the event §‡	Omit dose; when resolved to \leq Grade 2 within the same cycle, decrease one dose level.	Start at or maintain the decreased dose level.
Diarrhea		

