11.3.1. Tumor Imaging

Baseline tumor imaging (by CT scan, PET or MRI) has to be performed at screening within 28 days prior to the treatment start. On treatment, tumor assessments will be performed every even month (i.e., end of Cycle 2, 4, 6 etc) or whenever a clinical deterioration is observed and at the end of last cycle, unless a tumor assessment was performed within the previous 4 weeks. In patients withdrawn for causes other than disease progression, during follow up, regular tumor imaging assessments will be performed every 2 months, until PD or until a new antitumor therapy starts. On treatment, a time window of -2/+5 days is allowed.

Patients with responding tumors (complete or partial response) must have response confirmed at least 4 weeks after the first documentation of response.

CT scan is the desirable method for lesion measurement. MRI is acceptable provided that the size of the measurable lesion is twice the slice thickness of the MRI. MRI should be performed at pre-treatment in case of known or suspected CNS involvement.

According to RECIST, the same method and technique (CT scan or MRI) should be used to characterize each identified and reported lesion at baseline and during the following assessments.

Imaging-based evaluation should be preferred to clinical examination when both could be used to assess the antitumor effect of the treatment.

According to mRECIST, tumor assessment should be performed with the administration of intravenous contrast to obtain a dual-phase imaging of the liver. To prevent possibly allergic reactions to intravenous Contrast Medium (CM), patients with previous reaction(s) to CM, asthma even drug controlled and/or food or drug allergies will be treated with a premedication (corticosteroid).

Patients can be followed with either contrast-enhanced spiral CT (preferably with use of multi-slice scanners) or contrast-enhanced dynamic MRI. Each modality has advantages and disadvantages, and mRECIST does not recommend one modality over another.

However, it is recommended that the same imaging modality be used throughout the study. Ultrasound – including contrast-enhanced ultrasound – is not recommended for the general use of mRECIST.

PET/CT is not accepted for treatment assessment in guidelines.

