12.2. Definition of Analyzed Study Populations

The following analysis sets are defined according to ICH E9 guidelines [26].

Phase I Dose Escalation

Enrolled Set (ES): this population will include all patients who are enrolled in Phase I part, regardless of whether patients receive study treatment or not. This population will be evaluated in the analysis of patients' disposition.

Treated Set (TS): this set will include all enrolled patients who take at least one dose of NMS-01940153E. This population will be evaluated in the analysis of patients' disposition, baseline characteristics, treatment exposure, safety and efficacy.

Dose-Limiting Toxicity Evaluable Set (DLTES): this set will include all patients who receive in the first cycle at least 66% of study drug, unless the reason for non-compliance is drug-related toxicity, and undergo a DLT assessment within the DLT window. Patients not fulfilling one or more of aforementioned criteria will not be considered evaluable for MTD determination and will be substituted.

Phase II

Enrolled Set (ES): this population will include all patients enrolled in Phase II, regardless of whether patients receive study treatment or not. This population will be evaluated in the analysis of patients' disposition.

Treated Set (TS): this set will include all enrolled patients who actually receive at least one dose of NMS 01940153E. This population will be evaluated in the analysis of patients' disposition, baseline characteristics, treatment exposure and safety.

Evaluable Set (ES): this is the patient population for the primary efficacy analysis. This set will include patients of the TS who have measurable disease at baseline assessed according to RECIST 1.1 and at least one tumor evaluation on treatment, unless they die before the first tumor on-treatment assessment, in which case they will be considered treatment failure. In detail, the evaluable population for primary efficacy endpoint will consist of a subset of the evaluable population up to the total number of subjects pre-determined by the interim for futility and final analyses. This means that, if the number of evaluable subjects exceeds the planned total number of subjects at either stage, the exceeding subjects will not be considered for primary efficacy analysis. Subjects will be counted into the primary evaluable population, consecutively, based on the date of first NMS-01940153E administration.

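### SAP section 7 limits the protocol's rule on death before the first scan to 61 days, a day that ignores permitted cycle delays; the effect on ORR is minor and never downward

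*SAP*

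**What the plan says.** Protocol 12.2 admits to the Phase II Evaluable Set treated patients with measurable disease at baseline and at least one on-treatment tumour evaluation, with one exception: "unless they die before the first tumor on-treatment assessment, in which case they will be considered treatment failure". The synopsis (1.4, Analysis Sets) has the same rule. Neither gives a day.

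SAP 7 repeats the rule and adds a parenthesis, "i.e. if the patients died within 61 days from the start of the treatment". It explains the figure by the first scan being planned for the end of cycle 2, with a window of -2/+5 days.

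The passages that bear on that figure are:

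- Delays: patients who cannot be retreated "within 1 week from day 28 (up to day 35) will go off-treatment" (protocol 1.4), unless the investigator judges continuation to be in the patient's interest, in which case "a maximum delay of 2 weeks (up to day 42 from cycle start) will be allowed" (protocol 9.2.3.2).
- Imaging: scans are planned at the end of even cycles, "or whenever a clinical deterioration is observed and at the end of last cycle" (protocol 11.3.1).
- Change control: SAP 2.1 states that section 7 "was updated to add clarifications for the definition of Evaluable Set for Phase II portion based on protocol version 5.0". The SAP section headed "6. CHANGES IN THE PLANNED ANALYSIS" contains only a statement that it does not apply.
- Counting: "Subjects will be counted into the primary evaluable population, consecutively, based on the date of first NMS-01940153E administration", with patients above the planned number left out of the primary analysis (SAP 7; the same rule is in protocol 12.2).

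**The concern.** The Evaluable Set is the denominator of the primary ORR. A patient who dies without an on-treatment scan cannot be a responder, so whether such patients are in or out affects only the denominator. The protocol keeps them in. The SAP, taken literally, keeps only those who die by day 61.

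Two things look wrong. First, the day does not follow from the SAP's own reasoning once a cycle is delayed: a patient can die after day 61 with the first scan not yet due. Second, the limit is presented as a clarification of protocol version 5.0, which contains no such limit, so a reader of SAP 6 would not learn that the primary denominator differs from the protocol's. The analysis on the Treated Set that would show the difference is optional under SAP 9.7.

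**Working it through.** **1. Reproducing day 61.** Cycle length is 28 days (protocol 5.1) and the late edge of the imaging window is +5 days (protocol 11.3.1). 2 × 28 + 5 = 61. The SAP's figure reproduces, for undelayed cycles only.

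**2. The same sum with permitted delays.** If cycle 1 runs to day 35: 35 + 28 + 5 = 68. If it runs to day 42: 42 + 28 + 5 = 75. Day 61 is 7 to 14 days short.

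**3. Direction.** On this rule the SAP set is a subset of the protocol set, and each patient removed is a certain non-responder. If the place stays empty, the denominator shrinks. If it is refilled under the cap of 38, a certain failure is exchanged for a patient whose chance of response is at least zero. ORR cannot fall in either case.

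**4. Expected number of patients.** Inputs: median OS of 8 to 10 months after first-line failure (protocol 3.1), exponential survival (assumed), month = 30.44 days.

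P(death on days 62–75) = exp(−λ·61) − exp(−λ·75), with λ = ln 2 / (median × 30.44).

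| Median OS | P(days 62–75) | × 40 patients | P(days 62–68) | × 40 patients |
|---|---|---|---|---|
| 8 months | 0.0328 | 1.31 | 0.0166 | 0.66 |
| 10 months | 0.0273 | 1.09 | 0.0138 | 0.55 |

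Only patients never scanned on treatment are affected.

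- Unscanned share 10–50% (assumed): 1.09 × 0.1 = 0.11 to 1.31 × 0.5 = 0.66 patients of 40.
- Delayed cycle required as well, share 20–50% (assumed): 1.09 × 0.2 × 0.1 = 0.02 to 1.31 × 0.5 × 0.5 = 0.33.
- Shorter survival, since Phase II patients have already had a checkpoint inhibitor and a TKI: at a median of 6 months, 0.0411 × 40 = 1.64, and at 4 months, 0.0541 × 40 = 2.16. At an unscanned share of 50% these become 0.82 and 1.08.

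Never-scanned patients who die after day 75 come on top and are not estimated. The plan's own allowance for non-evaluable patients of any kind, 0.10 × 40 = 4, is a rough ceiling for the total, if it holds.

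**5. Effect per patient.** With 11 responders:

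| Denominator | ORR | Exact lower limit, one-sided 95% | Exact lower limit, two-sided 95% |
|---|---|---|---|
| 38 | 28.9% | 17.2% | 15.4% |
| 37 | 29.7% | 17.7% | 15.9% |
| 36 | 30.6% | 18.2% | 16.3% |

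That is about 0.8 points per exclusion. If the place is refilled at the assumed ORR of 0.30, the expected gain is 0.30/38 = 0.79 points. The expected shift is then 0.11 × 0.79 = 0.1 to 0.66 × 0.79 = 0.5 points. At the ceiling of 4 patients it would be 4 × 0.79 = 3.2 points, which is a bound and not an expectation.

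**6. Interim.** Among the first 10, 0.11/4 = 0.03 to 0.66/4 = 0.16 such patients are expected. At a true ORR of 18%, one exclusion changes the chance of a futility stop by 0.82⁹ − 0.82¹⁰ = 0.030. The expected change is at most 0.16 × 0.030 = 0.005, or 0.5 points.

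**The case against.** The strongest reply is that the protocol's wording is open. Death before the first assessment may mean death before the scan was due, not death at any later time without a scan. On the second meaning, almost every never-scanned patient would in time become a failure, because survival is followed until death and SAP 5.3 places the final analysis after follow-up ends. A cut-off at the scan-due date is therefore a defensible implementation, and protocol 12.3 leaves implementation to the SAP. This stands, but it does not rescue day 61: on the scan-due meaning the day is still wrong for any patient with a delayed cycle 1. The protocol's mention of even months alongside even cycles might suggest a calendar schedule, but the SAP bases its own figure on the end of cycle 2.

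The separate appendix on mock-ups and algorithms, which is not part of the documents reviewed, may deal with delayed cycles. The text of SAP 7 would still need to agree with it.

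The further objection, that the effect is small and rests largely on assumed shares, is accepted.

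A reader might infer more than the documents support:

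- **That the limit could turn a negative result positive.** The one-sided limit passes 18% between denominators 37 and 36 with 11 responders. But no success rule is tied to 18%, and SAP 9.7.1 does not say whether its 95% interval is one- or two-sided.
- **That DoR is distorted.** DoR concerns responders only, so removing never-scanned non-responders cannot change it. PFS and OS use the same set, but no direction or size is claimed for them.
- **That the futility look is weakened.** SAP 5.2 also asks for at least one on-treatment assessment, so never-scanned patients may be left out there regardless.

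**Conclusion.** The point holds as a minor but real discrepancy in the primary analysis set. SAP 7 puts a 61-day limit on a protocol rule that has none. The day is wrong on the SAP's own basis when cycle 1 is delayed, and SAP 6 does not declare the change. That ORR cannot fall as a result follows from the definitions and needs no assumption.

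The size does need assumptions: exponential survival, a median OS taken from patients who had failed first-line therapy, and assumed unscanned and delayed shares. Under these, deaths on days 62–75 probably affect fewer than one patient of 40. Only the extreme corner tried here (median OS 4 months, half of these deaths unscanned, no delayed cycle required) reaches about one. The effect is zero if no such death occurs. It is worth correcting because it concerns the primary denominator of a single-arm trial of about 38 evaluable patients and costs almost nothing to put right.

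**What to change.** In SAP 7, delete the parenthesis with the 61-day limit and state:

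> A treated patient with measurable disease at baseline who dies without any on-treatment tumour assessment is included in the Evaluable Set as a non-responder.

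Keep the existing cap and the consecutive counting by date of first dose.

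If a scan-due cut-off is what is meant, define it for each patient as the actual end of cycle 2, including permitted delays, plus 5 days. Give a fallback date for patients who never start or complete cycle 2, since they have no such date. List the cut-off in SAP 6 as a departure from protocol 12.2, in place of the present entry.

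The cost is a few lines of SAP text and no new data. ORR may be slightly lower. With the parenthesis deleted, a never-scanned patient alive at the interim may enter the set as a failure by the final analysis. Because the cap is kept, that patient takes the place given by the first-dose date, and the last patient counted may drop out. The scan-due option largely avoids this, but still leaves out never-scanned patients who die after their due date.
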